Hypoxia	xx(xx.x%)	xx(xx.x%)	xx(xx.x%)	xx(xx.x%)	xx(xx.x%)	xx (xx.x%
Hypotension	xx(xx.x%)	xx(xx.x%)	xx(xx.x%)	xx(xx.x%)	xx(xx.x%)	xx (xx.x%
Crampy Abdominal Pain	xx(xx.x%)	xx(xx.x%)	xx(xx.x%)	xx(xx.x%)	xx(xx.x%)	xx (xx.x%
Vomiting	xx(xx.x%)	xx(xx.x%)	xx(xx.x%)	xx(xx.x%)	xx(xx.x%)	xx (xx.x%
Diarrhoea	xx(xx.x%)	xx(xx.x%)	xx(xx.x%)	xx(xx.x%)	xx(xx.x%)	xx (xx.x%
Other	xx(xx.x%)	xx(xx.x%)	xx(xx.x%)	xx(xx.x%)	xx(xx.x%)	xx (xx.x%

. . .

N = number of subjects per treatment group.

Reference Listing: 16.2.9.9

Programming Notes:

- Display only Type of reaction with non-missing value.
- A column for column dosing (column dosing will only be added if Stage 4 is initiated.

Final 1 2 | 04-Oct-2023 | Page 114 of 218

[figure not shown]

[figure not shown]
Table 14.3.5.11 Summary of Liver Diagnostic Investigations Safety Population

	Placebo		MEDI7352			Total
		CCI	CCI	CCI	All MEDI7352	
Statistic or Category	(N=xx)	(N=xx)	(N=xx)	(N=xx)	(N=xx)	(N=xx)
Subjects with Liver Diagnostics Performed	xx (xx.x%)	xx (xx.x%)				
Type of Diagnostic Investigation						
Ültra sound	xx(xx.x%)	xx(xx.x%)	xx(xx.x%)	xx(xx.x%)	xx(xx.x%)	xx(xx.x%)
CT	xx(xx.x%)	xx (xx.x%)	xx(xx.x%)	xx (xx.x%)	xx(xx.x%)	xx(xx.x%)
MRI/MRCP	xx(xx.x%)	xx (xx.x%)	xx (xx.x%)	xx(xx.x%)	xx (xx.x%)	xx (xx.x%)
Flushing	xx(xx.x%)	xx (xx.x%)	xx (xx.x%)	xx(xx.x%)	xx(xx.x%)	xx(xx.x%)
ERCP	xx(xx.x%)	xx(xx.x%)	xx(xx.x%)	xx(xx.x%)	xx(xx.x%)	xx(xx.x%)
X-Ray	xx(xx.x%)	xx (xx.x%)	xx (xx.x%)	xx(xx.x%)	xx (xx.x%)	xx (xx.x%)
Tox Screening for	xx(xx.x%)	xx(xx.x%)	xx(xx.x%)	xx(xx.x%)	xx(xx.x%)	xx(xx.x%)
Acetaminophen/Paracetamol						
Tox Screening for Ethanol	xx(xx.x%)	xx(xx.x%)	xx(xx.x%)	xx(xx.x%)	xx(xx.x%)	xx(xx.x%)
Tox Screening, Other	xx(xx.x%)	xx(xx.x%)	xx(xx.x%)	xx(xx.x%)	xx(xx.x%)	xx(xx.x%)
Specialist Consulted	xx(xx.x%)	xx(xx.x%)	xx(xx.x%)	xx(xx.x%)	xx(xx.x%)	xx(xx.x%)
Serology for Hepatitis A	xx(xx.x%)	xx(xx.x%)	xx(xx.x%)	xx(xx.x%)	xx(xx.x%)	xx(xx.x%)
Serology for Hepatitis B	xx(xx.x%)	xx(xx.x%)	xx(xx.x%)	xx(xx.x%)	xx(xx.x%)	xx(xx.x%)
Serology for Hepatitis C	xx(xx.x%)	xx(xx.x%)	xx(xx.x%)	xx(xx.x%)	xx(xx.x%)	xx(xx.x%)
Serology for Hepatitis D	xx(xx.x%)	xx(xx.x%)	xx(xx.x%)	xx(xx.x%)	xx(xx.x%)	xx(xx.x%)
Serology for Hepatitis E	xx xx.x%)	xx xx.x%)				
Serology for Cytomegalovirus	xx(xx.x%)	xx(xx.x%)	xx(xx.x%)	xx(xx.x%)	xx(xx.x%)	xx(xx.x%)
Serology for Epstein Barr Virus	xx(xx.x%)	xx(xx.x%)	xx(xx.x%)	xx(xx.x%)	xx(xx.x%)	xx(xx.x%)
Autoimmune Serology	xx(xx.x%)	xx (xx.x%)	xx(xx.x%)	xx(xx.x%)	xx(xx.x%)	xx(xx.x%)
Other	xx (xx.x%)	xx (xx.x%)	xx(xx.x%)	xx (xx.x%)	xx (xx.x%)	xx (xx.x%)

CT = Computerized tomography; ERCP = Endoscopic retrograde cholangiopancreatography; MRI = Magnetic resonance imaging; MRCP = Magnetic resonance cholangiopancreatography; N = number of subjects per treatment group.

Reference Listing: 16.2.9.10

Final 1 2 | 04-Oct-2023 | Page 115 of 218

Programming Notes:

- Display only Diagnostic Investigations with non-missing value.
- A column for column dosing (column dosing will only be added if Stage 4 is initiated.

Final 1 2 | 04-Oct-2023 | Page 116 of 218

[figure not shown]
[figure not shown]

Table 14.3.5.12 Summary of Liver Risk Factors and Lifestyle Events Safety Population

	Placebo		MEDI7352			Total
		CCI	CCI	CCI	All MEDI7352	
Statistic or Category	(N=xx)	$\overline{(N=xx)}$	(N=xx)	(N=xx)	(N=xx)	(N=xx)
Cubicata with Liver Diely Footons	(0/)	(0/)	(0/)	(0/)	(0/)	(0/)
Subjects with Liver Risk Factors	xx (xx.x%)	xx(xx.x%)	xx(xx.x%)	xx (xx.x%)	xx(xx.x%)	xx (xx.x%)
Assessed						
Liver Risk Factor						
Alcohol Abuse	xx(xx.x%)	xx(xx.x%)	xx(xx.x%)	xx(xx.x%)	xx(xx.x%)	xx(xx.x%)
Increased Alcohol Consumption	xx (xx.x%)	xx (xx.x%)	xx (xx.x%)	xx(xx.x%)	xx(xx.x%)	xx (xx.x%)
within 1 Month of Reported Event						
IV Drug Abuse	xx(xx.x%)	xx(xx.x%)	xx(xx.x%)	xx(xx.x%)	xx(xx.x%)	xx(xx.x%)
Tattoo	xx (xx.x%)	xx (xx.x%)	xx (xx.x%)	xx (xx.x%)	xx(xx.x%)	xx (xx.x%)
Acupuncture	xx(xx.x%)	xx(xx.x%)	xx(xx.x%)	xx(xx.x%)	xx(xx.x%)	xx(xx.x%)
Sexually Transmitted Diseases	xx (xx.x%)	xx (xx.x%)	xx (xx.x%)	xx (xx.x%)	xx(xx.x%)	xx (xx.x%)
Toxic/Chemical Agent Exposure	xx(xx.x%)	xx(xx.x%)	xx(xx.x%)	xx(xx.x%)	xx(xx.x%)	xx(xx.x%)
Travel (Areas at Risk in the Last Year)	xx (xx.x%)					
Pregnancy	xx (xx.x%)	xx (xx.x%)	xx (xx.x%)	xx(xx.x%)	xx(xx.x%)	xx (xx.x%)
Parenteral Nutrition	xx(xx.x%)	xx(xx.x%)	xx(xx.x%)	xx(xx.x%)	xx(xx.x%)	xx(xx.x%)
Excessive Physical Exercise	xx (xx.x%)					
Changes Diet/Fasting Episodes/Weight	xx (xx.x%)	xx (xx.x%)	xx (xx.x%)	xx(xx.x%)	xx(xx.x%)	xx (xx.x%)
Loss Diet						
Previous Drug Reaction	xx(xx.x%)	xx(xx.x%)	xx(xx.x%)	xx(xx.x%)	xx(xx.x%)	xx(xx.x%)
Blood Transfusion	xx(xx.x%)	xx(xx.x%)	xx(xx.x%)	xx(xx.x%)	xx(xx.x%)	xx(xx.x%)
Patient Exposed to Anyone with		xx xx.x%)				
Jaundice in the Last Month						
History of Hypotension	xx(xx.x%)	xx(xx.x%)	xx(xx.x%)	xx (xx.x%)	xx(xx.x%)	xx(xx.x%)
Pregnancy Parenteral Nutrition Excessive Physical Exercise Changes Diet/Fasting Episodes/Weight Loss Diet Previous Drug Reaction Blood Transfusion Patient Exposed to Anyone with Jaundice in the Last Month	xx (xx.x%) xx (xx.x%) xx (xx.x%) xx (xx.x%) xx (xx.x%) xx (xx.x%) xx (xx.x%)	xx (xx.x%) xx (xx.x%) xx (xx.x%) xx (xx.x%) xx (xx.x%) xx (xx.x%) xx (xx.x%)	xx (xx.x%) xx (xx.x%) xx (xx.x%) xx (xx.x%) xx (xx.x%) xx (xx.x%) xx (xx.x%)	xx (xx.x%) xx (xx.x%) xx (xx.x%) xx (xx.x%) xx (xx.x%) xx (xx.x%) xx (xx.x%)	xx (xx.x%) xx (xx.x%) xx (xx.x%) xx (xx.x%) xx (xx.x%) xx (xx.x%) xx (xx.x%)	xx (xx.x%) xx (xx.x%) xx (xx.x%) xx (xx.x%) xx (xx.x%) xx (xx.x%) xx (xx.x%)

Final 1 2 | 04-Oct-2023 | Page 117 of 218

Low Blood Pressure at Time of Event of Liver Injury and/or Abnormal Liver	xx (xx.x%)					
Laboratory Value				,		
History of Liver Disease Other	xx (xx.x%) xx (xx.x%)					

IV = intravenous; N = number of subjects per treatment group.

Reference Listing: 16.2.9.10

Programming Notes:

- Display only Liver Risk Factor with non-missing value.
- A column for column dosing (column dosing will only be added if Stage 4 is initiated.

Final 1 2 | 04-Oct-2023 | Page 118 of 218

[figure not shown]

[figure not shown]

Table 14.3.5.13 Summary of Liver Signs and Symptoms Safety Population

		Safety Popt				
	Placebo		MEDI7352			Total
		CCI	CCI	CCI	All MEDI7352	
Statistic or Category	(N=xx)	$\overline{(N=xx)}$	(N=xx)	(N=xx)	(N=xx)	(N=xx)
Cultipate with Liver Ciana/Cymraters	((0/)	(0/)	(0/)	(0/)	(0/)
Subjects with Liver Signs/Symptoms	xx (xx.x%)	xx(xx.x%)	xx(xx.x%)	xx(xx.x%)	xx (xx.x%)	xx (xx.x%)
Assessed						
Liver Sign/Symptom						
Anorexia	xx(xx.x%)	xx(xx.x%)	xx(xx.x%)	xx(xx.x%)	xx(xx.x%)	xx(xx.x%)
Asthenia	xx(xx.x%)	xx (xx.x%)	xx (xx.x%)	xx(xx.x%)	xx(xx.x%)	xx (xx.x%)
Pyrexia	xx(xx.x%)	xx(xx.x%)	xx(xx.x%)	xx(xx.x%)	xx(xx.x%)	xx (xx.x%)
Pruritus	xx(xx.x%)	xx(xx.x%)	xx (xx.x%)	xx(xx.x%)	xx(xx.x%)	xx (xx.x%)
Jaundice	xx(xx.x%)	xx (xx.x%)	xx (xx.x%)	xx(xx.x%)	xx (xx.x%)	xx (xx.x%)
Arthra lgia	xx(xx.x%)	xx(xx.x%)	xx(xx.x%)	xx(xx.x%)	xx(xx.x%)	xx(xx.x%)
Abdominal Pain	xx(xx.x%)	xx (xx.x%)	xx (xx.x%)	xx(xx.x%)	xx (xx.x%)	xx (xx.x%)
Abdominal Tenderness	xx(xx.x%)	xx(xx.x%)	xx(xx.x%)	xx(xx.x%)	xx(xx.x%)	xx(xx.x%)
Nausea	xx(xx.x%)	xx (xx.x%)	xx (xx.x%)	xx(xx.x%)	xx (xx.x%)	xx (xx.x%)
Vomiting	xx (xx.x%)	xx (xx.x%)	xx (xx.x%)	xx(xx.x%)	xx (xx.x%)	xx (xx.x%)
Rash	xx(xx.x%)	xx(xx.x%)	xx(xx.x%)	xx(xx.x%)	xx(xx.x%)	xx(xx.x%)
Mucosal Inflammation	xx(xx.x%)	xx (xx.x%)	xx (xx.x%)	xx(xx.x%)	xx (xx.x%)	xx (xx.x%)
Purpura	xx (xx.x%)	xx (xx.x%)	xx (xx.x%)	xx(xx.x%)	xx(xx.x%)	xx (xx.x%)
Hepatomegaly	xx(xx.x%)	xx(xx.x%)	xx(xx.x%)	xx(xx.x%)	xx(xx.x%)	xx(xx.x%)
Splenomegaly	xx xx.x%)	xx xx.x%)	xx xx.x%)	xx xx.x%)	xx xx.x%)	xx xx.x%)
Lymphadenopathy	xx(xx.x%)	xx(xx.x%)	xx(xx.x%)	xx(xx.x%)	xx(xx.x%)	xx(xx.x%)
Ascites	xx(xx.x%)	xx (xx.x%)	xx (xx.x%)	xx(xx.x%)	xx (xx.x%)	xx (xx.x%)
Confusional State	xx(xx.x%)	xx(xx.x%)	xx(xx.x%)	xx(xx.x%)	xx(xx.x%)	xx(xx.x%)
Coma	xx(xx.x%)	xx(xx.x%)	xx(xx.x%)	xx(xx.x%)	xx(xx.x%)	xx(xx.x%)
Upper Quadrant Tenderness	xx xx.x%)	xx xx.x%)	xx xx.x%)	xx xx.x%)	xx xx.x%)	xx xx.x%)
Biliary Obstruction	xx(xx.x%)	xx(xx.x%)	xx(xx.x%)	xx(xx.x%)	xx(xx.x%)	xx(xx.x%)
Eosinophilia	xx(xx.x%)	xx(xx.x%)	xx(xx.x%)	xx(xx.x%)	xx(xx.x%)	xx(xx.x%)
Dark Urine	xx(xx.x%)	xx (xx.x%)	xx (xx.x%)	xx (xx.x%)	xx(xx.x%)	xx (xx.x%)
Other	xx(xx.x%)	xx(xx.x%)	xx(xx.x%)	xx (xx.x%)	xx(xx.x%)	xx (xx.x%)
	` /	` /	` /	` ,	,	` /

N = number of subjects per treatment group.

Reference Listing: 16.2.9.12

Programming Notes:

- Display only Liver Signs/Symptoms with non-missing value.
- A column for column dosing (column dosing will only be added if Stage 4 is initiated.

Final 1 2 | 04-Oct-2023 | Page 120 of 218

[figure not shown]

Table 14.3.5.14 Summary of Infection Diagnostic Investigations Safety Population

	Placebo		MEDI7352			Total
Statistic or Category	(N=xx)	CCI (N=xx)	(N=xx)	CCI (N=xx)	All MEDI7352 (N=xx)	(N=xx)
Subjects with Infection Diagnostic Investigations	xx (xx.x%)	xx (xx.x%)	xx (xx.x%)	xx (xx.x%)	xx (xx.x%)	xx (xx.x%)
Method						
Microscopy, Culture and Sensitivity	xx(xx.x%)	xx(xx.x%)	xx(xx.x%)	xx (xx.x%)	xx(xx.x%)	xx(xx.x%)
Serological Tests	xx(xx.x%)	xx(xx.x%)	xx(xx.x%)	xx(xx.x%)	xx(xx.x%)	xx(xx.x%)
Nucleic Acid Based Tests	xx(xx.x%)	xx(xx.x%)	xx(xx.x%)	xx(xx.x%)	xx(xx.x%)	xx(xx.x%)
X-Ray	xx (xx.x%)	xx(xx.x%)	xx(xx.x%)	xx(xx.x%)	xx(xx.x%)	xx (xx.x%)
Other	xx(xx.x%)	xx (xx.x%)	xx (xx.x%)	xx(xx.x%)	xx(xx.x%)	xx(xx.x%)

N = number of subjects per treatment group. Reference Listing: 16.2.9.13

Programming Notes:

- Display only Methods with non-missing value.
- A column for column dosing (cc)) will only be added if Stage 4 is initiated.

Final 1.2 | 04-Oct-2023 Page 121 of 218

[figure not shown]

Table 14.3.5.15
Summary of Infection Risk Factors and Lifestyle Events
Safety Population

	Placebo	•	MEDI7352			Total
Statistic or Category	(N=xx)	CCI (N=xx)	CCI (N=xx)	CCI (N=xx)	All MEDI7352 (N=xx)	(N=xx)
Subjects with Infection Risk Factor Occurred	xx (xx.x%)	xx (xx.x%)	xx (xx.x%)	xx (xx.x%)	xx (xx.x%)	xx (xx.x%)
Infection risk factor						
Extensive Burns within the Last Year	xx(xx.x%)	xx(xx.x%)	xx(xx.x%)	xx(xx.x%)	xx(xx.x%)	xx (xx.x%)
Tattoo, Piercing or Acupuncture within the	xx(xx.x%)	xx(xx.x%)	xx(xx.x%)	xx (xx.x%)	xx (xx.x%)	xx (xx.x%)
last Year	,	, ,	,	,	, ,	,
Sexually Transmitted Diseases	xx(xx.x%)	xx(xx.x%)	xx(xx.x%)	xx(xx.x%)	xx(xx.x%)	xx (xx.x%)
Travel to Areas at Risk of Tuberculosis or	xx(xx.x%)	xx (xx.x%)	xx (xx.x%)	xx(xx.x%)	xx (xx.x%)	xx (xx.x%)
Tropical Diseases	,	,	, ,		, ,	
Infections Related to Travel	xx(xx.x%)	xx(xx.x%)	xx(xx.x%)	xx(xx.x%)	xx(xx.x%)	xx (xx.x%)
Blood Transfusion (within the Last Year)	xx (xx.x%)	xx(xx.x%)	xx (xx.x%)	xx (xx.x%)	xx (xx.x%)	xx (xx.x%)
Exposure to Nosocomial Pathogens within the	xx(xx.x%)	xx(xx.x%)	xx(xx.x%)	xx(xx.x%)	xx (xx.x%)	xx (xx.x%)
Last Year	,	, , , ,		, , ,		ì
Contact History with Infection Source	xx(xx.x%)	xx(xx.x%)	xx(xx.x%)	xx(xx.x%)	xx(xx.x%)	xx (xx.x%)
Previous BCG Immunization	xx(xx.x%)	xx (xx.x%)	xx (xx.x%)	xx(xx.x%)	xx (xx.x%)	xx (xx.x%)
Evidence of BCG Scar	xx (xx.x%)	xx(xx.x%)	xx (xx.x%)	xx (xx.x%)	xx (xx.x%)	xx (xx.x%)
Tuberculin Skin or Quantiferon Test Confirms	xx (xx.x%)	xx (xx.x%)	xx (xx.x%)	xx (xx.x%)	xx (xx.x%)	xx (xx.x%
Previous Exposure or Immunity to						
Tuberculosis						

BCG = Bacillus Calmette-Guerin; N = number of subjects per treatment group. Reference Listing: 16.2.9.14

Programming Notes:

- Display only infection risk factors with non-missing value.
- A column for column for column dosing (column for column for col

Final 1 2 | 04-Oct-2023 | Page 122 of 218

[figure not shown]
[figure not shown]

Table 14.3.5.16 Summary of Infection Signs and Symptoms Safety Population

Placebo		MEDI7352			Total
	CCI	CCI	CCI	All MEDI7352	
Statistic or Category (N=xx)	(N=xx)	(N=xx)	(N=xx)	(N=xx)	(N=xx)
Subjects with Infection Sign/Symptom xx (xx.x%)	xx (xx.x%)	xx (xx.x%)	xx (xx.x%)	xx (xx.x%)	xx (xx.x%)
Occurred Ax (Ax.X76)	AA (AA.A.70)	AA (AA.A70)	AA (AA.A70)	AA (AA.A70)	AA (AA.A70)
Infection Sign/Symptoms					
Pyrexia xx (xx.x%)	xx(xx.x%)	xx(xx.x%)	xx(xx.x%)	xx(xx.x%)	xx(xx.x%)
Headache xx (xx.x%)	xx(xx.x%)	xx (xx.x%)	xx (xx.x%)	xx (xx.x%)	xx (xx.x%)
Confusional State xx (xx.x%)	xx(xx.x%)	xx (xx.x%)	xx (xx.x%)	xx(xx.x%)	xx(xx.x%)
Convulsion $xx (xx.x\%)$	xx(xx.x%)	xx (xx.x%)	xx (xx.x%)	xx(xx.x%)	xx (xx.x%)
Rhinitis $xx (xx.x\%)$	xx(xx.x%)	xx (xx.x%)	xx (xx.x%)	xx(xx.x%)	xx(xx.x%)
Oropharyngeal Pain xx (xx.x%)	xx(xx.x%)	xx(xx.x%)	xx(xx.x%)	xx(xx.x%)	xx(xx.x%)
Cough $xx(xx.x\%)$	xx (xx.x%)	xx (xx.x%)	xx (xx.x%)	xx (xx.x%)	xx(xx.x%)
Productive Cough $xx (xx.x\%)$	xx(xx.x%)	xx(xx.x%)	xx(xx.x%)	xx(xx.x%)	xx(xx.x%)
Haemoptysis xx (xx.x%)	xx(xx.x%)	xx(xx.x%)	xx (xx.x%)	xx(xx.x%)	xx (xx.x%)
Wheezing $xx (xx.x\%)$	xx(xx.x%)	xx(xx.x%)	xx (xx.x%)	xx(xx.x%)	xx(xx.x%)
Dyspnoea xx (xx.x%)	xx(xx.x%)	xx(xx.x%)	xx(xx.x%)	xx(xx.x%)	xx(xx.x%)
Pleuritic Pain xx (xx.x%)	xx(xx.x%)	xx (xx.x%)	xx (xx.x%)	xx(xx.x%)	xx (xx.x%)
Vomiting $xx (xx.x\%)$	xx(xx.x%)	xx(xx.x%)	xx (xx.x%)	xx(xx.x%)	xx(xx.x%)
Diarrhoea $xx (xx.x\%)$	xx(xx.x%)	xx(xx.x%)	xx(xx.x%)	xx(xx.x%)	xx(xx.x%)
Genital Discharge xx (xx.x%)	xx(xx.x%)	xx(xx.x%)	xx (xx.x%)	xx(xx.x%)	xx (xx.x%)
Haematuria xx (xx.x%)	xx(xx.x%)	xx (xx.x%)	xx (xx.x%)	xx(xx.x%)	xx(xx.x%)
Dysuria $xx (xx.x\%)$	xx(xx.x%)	xx (xx.x%)	xx (xx.x%)	xx(xx.x%)	xx (xx.x%)
Hepatosplenomegaly $xx (xx.x\%)$	xx(xx.x%)	xx (xx.x%)	xx (xx.x%)	xx(xx.x%)	xx (xx.x%)
Jaundice xx (xx.x%)	xx(xx.x%)	xx(xx.x%)	xx (xx.x%)	xx(xx.x%)	xx(xx.x%)
Lymphadenopathy xx (xx.x%)	xx(xx.x%)	xx (xx.x%)	xx (xx.x%)	xx (xx.x%)	xx (xx.x%)

Final 1 2 | 04-Oct-2023 | Page 123 of 218

Rash	xx (xx.x%)	xx(xx.x%)	xx(xx.x%)	xx(xx.x%)	xx(xx.x%)
Petechial	xx (xx.x%)	xx(xx.x%)	xx(xx.x%)	xx(xx.x%)	xx(xx.x%)
Vesicular	xx (xx.x%)	xx(xx.x%)	xx(xx.x%)	xx(xx.x%)	xx(xx.x%)
Macular	xx (xx.x%)	xx(xx.x%)	xx(xx.x%)	xx(xx.x%)	xx(xx.x%)
Papular	xx (xx.x%)	xx(xx.x%)	xx(xx.x%)	xx(xx.x%)	xx(xx.x%)
Urticaria	xx (xx.x%)	xx(xx.x%)	xx(xx.x%)	xx(xx.x%)	xx(xx.x%)
Erythema	xx (xx.x%)	xx(xx.x%)	xx(xx.x%)	xx(xx.x%)	xx(xx.x%)
Blanching	xx (xx.x%)	xx(xx.x%)	xx(xx.x%)	xx(xx.x%)	xx(xx.x%)
Splinter Haemorrhages	xx (xx.x%)	xx(xx.x%)	xx(xx.x%)	xx(xx.x%)	xx(xx.x%)
Night sweats	xx (xx.x%)	xx(xx.x%)	xx(xx.x%)	xx(xx.x%)	xx(xx.x%)
Chills	xx (xx.x%)	xx(xx.x%)	xx(xx.x%)	xx(xx.x%)	xx(xx.x%)
Myalgia	xx (xx.x%)	xx(xx.x%)	xx(xx.x%)	xx(xx.x%)	xx(xx.x%)
Weight Decrease	xx (xx.x%)				

N = number of subjects per treatment group.

Reference Listing: 16.2.9.15

Programming Notes:

- Display only infection Signs/Symptoms with non-missing value.
- A column for column dosing (column dosing will only be added if Stage 4 is initiated.

Final 1.2 | 04-Oct-2023 | Page 124 of 218

[figure not shown]

Table 14.3.5.17 Summary of Concomitant Medications by ATC Level 2 and Preferred Name Safety Population

Programming Notes:

- Same shell as Table 14.1.7.
- Change footnote Note by: "Note: Concomitant medications are defined as medications continuing or starting on or after first dose of study medication. All concomitant medications are coded using WHO drug dictionary version vMar2023. At each level of summarization (ATC Level 2 or Preferred Name), subjects who reported more than one concomitant medication were only counted once. ATC Level 2 and Preferred Name are sorted in in descending order of frequency of total, and alphabetically if same frequency".
- If uncoded ATC Level or Preferred Name, please put them as [Not Coded]
- ATC and Preferred Name texts should be in proper case in table.
- A column for column for dosing (column for dosing

Final 1 2 | 04-Oct-2023 | Page 125 of 218

[figure not shown]

Table 14.3.5.18
Summary of Concomitant Procedures
Safety Population

System Organ Class	Placebo	MEDI7352			Total
Preferred Term	(N=xxx)	CCI (N=xx)	(N=xx)	(N=xx)	(N=xxx)
Any Concomitant Procedure	xx (xx.x %)	xx (xx.x %)	xx (xx.x %)	xx (xx.x %)	xx (xx.x %)
System Organ Class 1	xx (xx.x %)	xx (xx.x %)	xx (xx.x %)	xx (xx.x %)	xx (xx.x %)
Preferred Term 1	xx (xx.x %)	xx (xx.x %)	xx (xx.x %)	xx (xx.x %)	xx (xx.x %)
Preferred Term n	xx (xx.x %)	xx (xx.x %)	xx (xx.x %)	xx (xx.x %)	xx (xx.x %)
•••					
System Organ Class n	xx (xx.x %)	xx (xx.x %)	xx (xx.x %)	xx (xx.x %)	xx (xx.x %)
Preferred Term 1	xx (xx.x %)	xx (xx.x %)	xx (xx.x %)	xx (xx.x %)	xx (xx.x %)
Preferred Term n	xx (xx.x %)	xx (xx.x %)	xx (xx.x %)	xx (xx.x %)	xx (xx.x %)

N = number of subjects per treatment group; PT = Preferred Term; SOC = System Organ Class.

Note: All Procedure terms were coded using the Medical Dictionary for Regulatory Activities (MedDRA), version 26.0. At each level of summarization (system organ class or preferred term), subjects having more than one Procedure term were counted only once. System organ class and preferred terms are sorted in descending order of frequency of Total column, and alphabetically if same frequency.

When there are uncoded Procedure Events in the database, the events will be summarized with SOC and PT set to [Not Coded]. The [Not Coded] are sorted at the end of the table.

Reference Listing: 16.2.9.18

Programming Notes:

- SOC and PT texts should be in proper case in table.
- Sort SOC and PT (within SOC) in descending order of frequency in the Total column. Sort alphabetically in case of ties.
- Uncoded Procedure events
 - When there are uncoded Procedure Events in the database, the events will be summarized with SOC and PT set to [Not Coded]. The [Not Coded] will be sorted at the end of the table.
- A column for column dosing (column dosing will only be added if Stage 4 is initiated.

Final 1 2 | 04-Oct-2023 | Page 126 of 218

[figure not shown]

Table 14.3.5.19
Anti-Drug Antibody Results and Titre Summary by Timepoint Safety Population

	Placebo	•	MEDI	[7352	
Visit/ Statistic	(N=xx)	CCI (N=xx)	CCI (N=xx)	CCI (N=xx)	All MEDI7352 (N=xx)
Baseline [1]					
n [2]	XX	XX	XX	XX	XX
ADA Positive: n (%) [3]	xx(xx.x%)	xx(xx.x%)	xx(xx.x%)	xx(xx.x%)	xx(xx.x%)
ADA Titre		, ,	,	, ,	, ,
Median	XX.X	XX.X	XX.X	XX.X	XX.X
Q1, Q3	XX.X, XX.X	XX.X, XX.X	XX.X, XX.X	XX.X, XX.X	XX.X, XX.X
Min, Max	xx, xx	xx, xx	xx, xx	XX, XX	xx, xx
Week 2					
n [2]	XX	XX	XX	XX	XX
ADA Positive: n (%) [3]	xx(xx.x%)	xx(xx.x%)	xx(xx.x%)	xx(xx.x%)	xx(xx.x%)
ADA Titre					
Median	XX.X	XX.X	XX.X	XX.X	XX.X
Q1, Q3	XX.X, XX.X	XX.X, XX.X	XX.X, XX.X	XX.X, XX.X	XX.X, XX.X
Min, Max	XX, XX	XX, XX	XX, XX	XX, XX	XX, XX

ADA = Anti-Drug Antibodies; N = number of subjects per treatment group; SD = standard deviation; Q1 = first quartile; Q3 = third quartile.

Reference Listing: 16.2.9.19

Programming Notes:

- Keep in mind that in this table 'Total' column does not include placebo.
- Repeat for all scheduled post-baseline visits.
- A column for column for dosing (column for dosing

Final 1 2 | 04-Oct-2023 | Page 127 of 218

^[1] Baseline is defined as the last observation recorded prior to the first dose of treatment.

^[2] Number of subjects with at least one ADA assessment at the specific visit.

^[3] Number of subjects with a positive result at the specific visit. The denominator for all percentages is the number of subjects with an ADA result for each visit.

[figure not shown]
[figure not shown]

Table 14.3.5.20
Descriptive Summary of Anti-Drug Antibody Results and Titre by ADA Categories
Safety Population

	Placebo	y Population	MED	I7352	
ADA Category	(N=xx)	CCI (N=xx)	(N=xx)	CCI (N=xx)	All MEDI7352 (N=xx)
ADA positive at baseline and/or post-baseline (ADA					
prevalence)					
n/Nobs (%) [1] [2]	xx/xxx(xx.x%)	xx/xxx(xx.x%)	xx/xxx(xx.x%)	xx/xxx(xx.x%)	xx/xxx(xx.x%)
Maximum ADA Titre					
Median	XX.X	XX.X	XX.X	XX.X	XX.X
Q1, Q3	XX.X, XX.X				
Min, Max	XX, XX				
TE-ADA positive (ADA incidence) [5]					
n/Nobs (%) [1] [3]	xx/xxx(xx.x%)	xx/xxx(xx.x%)	xx/xxx(xx.x%)	xx/xxx(xx.x%)	xx/xxx(xx.x%)
Maximum ADA Titre	,	,	,	,	,
Median	XX.X	XX.X	XX.X	XX.X	XX.X
Q1, Q3	XX.X, XX.X				
Min, Max	XX, XX				
Treatment Induced ADA Positive					
n/Nobs (%) [1] [3]	xx/xxx(xx.x%)	xx/xxx(xx.x%)	xx/xxx(xx.x%)	xx/xxx(xx.x%)	xx/xxx(xx.x%)
Maximum ADA Titre	,	•	,	,	· · · ·
Median	XX.X	XX.X	XX.X	XX.X	XX.X
Q1, Q3	XX.X, XX.X				
Min, Max	XX, XX				

[figure not shown]
Final 1 2 | 04-Oct-2023 | Page 128 of 218

Treatment-Boosted ADA Positive n/Nobs (%) [1] [3]	xx/xxx (xx.x%)				
Maximum ADA Titre					
Median	XX.X	XX.X	XX.X	XX.X	XX.X
Q1, Q3	XX.X, XX.X				
Min, Max	XX, XX				
Non-TE-ADA Positive [6]					
n/Nobs (%) [1] [3]	xx/xxx(xx.x%)	xx/xxx(xx.x%)	xx/xxx(xx.x%)	xx/xxx(xx.x%)	xx/xxx(xx.x%)
Maximum ADA Titre					
Median	XX.X	XX.X	XX.X	XX.X	XX.X
Q1, Q3	XX.X, XX.X				
Min, Max	xx, xx				
Both baseline and post-baseline positive					
n/Nobs (%) [1] [3]	xx/xxx(xx.x%)	xx/xxx(xx.x%)	xx/xxx(xx.x%)	xx/xxx(xx.x%)	xx/xxx(xx.x%)
Maximum ADA Titre					
Median	XX.X	XX.X	XX.X	XX.X	XX.X
Q1, Q3	XX.X, XX.X				
Min, Max	xx, xx				
Only baseline positive					
n/Nobs (%) [1] [4]	xx/xxx(xx.x%)	xx/xxx(xx.x%)	xx/xxx(xx.x%)	xx/xxx(xx.x%)	xx/xxx(xx.x%)
Maximum ADA Titre					
Median	XX.X	XX.X	XX.X	XX.X	XX.X
Q1, Q3	XX.X, XX.X				
Min, Max	xx, xx				
TE-persistently ADA positive [7]					
n/Nobs (%) [1] [3]	xx/xxx(xx.x%)	xx/xxx(xx.x%)	xx/xxx(xx.x%)	xx/xxx(xx.x%)	xx/xxx(xx.x%)
Maximum ADA Titre					
Median	XX.X	XX.X	XX.X	XX.X	XX.X
Q1, Q3	XX.X, XX.X				
Min, Max	XX, XX				

Final 1 2 | 04-Oct-2023 | Page 129 of 218

TE-transiently ADA positive [8]
n/Nobs (%) [1] [3]
Maximum ADA Titre
Median
Q1, Q3
Min, Max

xx/xxx ($xx.x%$)	xx/xxx ($xx.x%$)	xx/xxx(xx.x%)	xx/xxx ($xx.x%$)	xx/xxx (xx.x%)
XX.X	XX.X	XX.X	XX.X	XX.X
XX.X, XX.X	XX.X, XX.X	XX.X, XX.X	XX.X, XX.X	XX.X, XX.X
xx, xx	XX, XX	xx, xx	xx, xx	xx, xx

[figure not shown]
ADA = Anti-Drug Antibodies; N=number of subjects per treatment group; TE-ADA = Treatment Emergent ADA; SD = standard deviation; Q1 = first quartile; Q3 = third quartile.

- [1] n represents the number of subjects satisfying the conditions of the specified ADA category
- [2] Nobs represents the number of subjects with any ADA result at baseline and/or post-baseline.
- [3] Nobs represents the number of subjects with an ADA result at baseline and at least one post-baseline ADA assessment.
- [4] Nobs represents the number of subjects with an ADA result at baseline.
- [5] TE-ADA positive is defined as either ADA negative at baseline and post-baseline ADA positive (Treatment Induced ADA Positive), or as ADA positive at baseline with pre-existing titre boosted by 4-fold or greater during the study period (Treatment-boosted ADA Positive). ADA incidence is the proportion of TE-ADA+ subjects in a population.
- [6] ADA post-baseline positive but not fulfilling the conditions for TE-ADA+
- [7] ADA negative at baseline and having at least 2 post-baseline ADA positive measurements with ≥16 weeks (112 days) between first and last positive, or an ADA positive result at the last available post-baseline assessment.
- [8] ADA negative at baseline and at least one post-baseline ADA positive measurement and not fulfilling the conditions for persistently positive.

Reference Listing: 16.2.9.19

Programming Notes:

- If a participant has more than 1 non-missing titre during the study, the maximum titre for each participant is summarized.
- Only present summary statistics if titre is available.
- If no positive results for a particular block of the table, then the summary statistics for the titres for that particular block would not appear.
- It is assumed that participants with a missing baseline ADA result are ADA negative at baseline.
- A column for column dosing (column dosing will only be added if Stage 4 is initiated.

7. Pharmacokinetic/Pharmacodynamic Data

Table 14.4.1 Summary of Serum MEDI7352 Concentrations PK Population

ADA Status: xxxxxxxxxx

[figure not shown]
		MEDI7352	
Visit/	CCI	CCI	CCI
Statistic	$\overline{(N=xx)}$	$\overline{(N=xx)}$	(N=xx)
Baseline [1]			
n (n < LLOQ)	xx (xx)	xx (xx)	xx (xx)
Mean (SD)	xx.x (xx.xx)	xx.x (xx.xx)	xx.x (xx.xx)
gMean $[gMean \pm gSD]$	x.xx[x.xx to x.xx]	x.xx [x.xx to x.xx]	x.xx[x.xx to x.xx]
gCV%	XX.X	XX.X	XX.X
Median	XX.X, XX.X	XX.X, XX.X	XX.X, XX.X
Min, Max	XX, XX	XX, XX	XX, XX
Week 2			
n (n < LLOQ)	xx (xx)	xx (xx)	xx (xx)
Mean (SD)	xx.x (xx.xx)	xx.x (xx.xx)	xx.x (xx.xx)
gMean [gMean \pm gSD]	x.xx[x.xx to x.xx]	x.xx [x.xx to x.xx]	x.xx [x.xx to x.xx]
gCV%	XX.X	XX.X	XX.X
Median	XX.X, XX.X	XX.X, XX.X	XX.X, XX.X
Min, Max	XX, XX	xx, xx	XX, XX
Week 4			
n (n < LLOQ)	xx(xx)	xx (xx)	xx(xx)
Mean (SD)	xx.x (xx.xx)	xx.x (xx.xx)	xx.x (xx.xx)
gMean [gMean ± gSD]	x.xx[x.xx to x.xx]	x.xx[x.xx to x.xx]	x.xx [x.xx to x.xx]
gCV%	XX.X	XX.X	XX.X
Median	XX.X, XX.X	XX.X, XX.X	XX.X, XX.X
Min, Max	XX, XX	XX, XX	XX, XX

gCV% = Geometric Coefficient of Variation (%); gMean = Geometric Mean; gSD = Geometric SD; LLOQ = Lower Limit of Quantification; n = number of subjects by treatment group at each visit for the parameter; N = number of subjects per treatment group; NC = not calculable; NQ = not quantifiable. [1] Baseline is defined as the last observation recorded prior to the first dose of treatment.

Note: serum MEDI7352 concentration units = ng/mL

Reference Listing: 16.2.10.1

Final 1 2 | 04-Oct-2023 | Page 131 of 218

Programming Notes:

- Include the following timepoints: Baseline (Day 1), Week 2, Week 4, Week 6, Week 8, Week 10: Pre-Dose, Week 10; Before End of Infusion, Week 10: 8 Hours after Infusion, Week 10 + 24 hours/ Pre-Dose, Week 11/ Pre-Dose, Week 10 + 14 Days/Pre-Dose; Week 18.
- Repeat the table for 'ADA Positive', 'ADA Negative' and 'Overall'.
- Any values reported as NRR (not reportable) or NS (missing) will be excluded from the summary tables.
- At a time point where less than or equal to 50% of the concentration values are NQ (below LLOQ), all NQ values will be set to the LLOQ, and all descriptive statistics will be calculated accordingly.
- At a time point where more than 50% (but not all) of the values are NQ, the gmean, gmean ± gSD and gCV% will be set to NC. The maximum value will be reported from the individual data, and the minimum and median will be set to NQ.
- If all concentrations are NQ at a time point, no descriptive statistics will be calculated for that time point. The gmean, minimum, median and maximum will be reported as NQ and the gCV% and gmean ± gSD as NC.

Final 1.2 | 04-Oct-2023 | Page 132 of 218

[figure not shown]

Table 14.4.2 Summary of Serum total NGF Concentrations Safety Population

ADA Status: xxxxxxxxxx

[figure not shown]
	Placebo		MEDI7352	
Visit/		CCI	CCI	CCI
Statistic	(N=xx)	(N=xx)	(N=xx)	(N=xx)
Baseline [1]				
n (n < LLOQ)	xx (xx)	xx (xx)	xx (xx)	xx(xx)
Mean (SD)	xx.x (xx.xx)	xx.x (xx.xx)	xx.x (xx.xx)	xx.x (xx.xx)
gMean $[gMean \pm gSD]$	x.xx[x.xx to x.xx]	x.xx [x.xx to x.xx]	x.xx[x.xx to x.xx]	,
gCV%	XX.X	XX.X	XX.X	XX.X
Median	XX.X, XX.X	xx.x, xx.x	XX.X, XX.X	XX.X, XX.X
Min, Max	XX, XX	XX, XX	XX, XX	xx, xx
Week 2				
n (n < LLOQ)	xx (xx)	xx (xx)	xx (xx)	xx(xx)
Mean (SD)	xx.x (xx.xx)	xx.x (xx.xx)	xx.x (xx.xx)	xx.x (xx.xx)
gMean [gMean \pm gSD]	x.xx[x.xx to x.xx]	x.xx[x.xx to x.xx]	x.xx[x.xx to x.xx]	, ,
gCV%	XX.X	XX.X	XX.X	XX.X
Median	XX.X, XX.X	XX.X, XX.X	XX.X, XX.X	XX.X, XX.X
Min, Max	XX, XX	XX, XX	XX, XX	XX, XX
Week 4				
n (n < LLOQ)	xx (xx)	xx (xx)	xx (xx)	xx(xx)
Mean (SD)	xx.x (xx.xx)	xx.x (xx.xx)	xx.x (xx.xx)	xx.x (xx.xx)
gMean [gMean \pm gSD]	x.xx[x.xx to x.xx]	x.xx [x.xx to x.xx]	x.xx [x.xx to x.xx]	` '
gCV%	XX.X	XX.X	xx.x	XX.X
Median	XX.X, XX.X	xx.x, xx.x	XX.X, XX.X	XX.X, XX.X
Min, Max	xx, xx	xx, xx	xx, xx	XX, XX

gCV% = Geometric Coefficient of Variation (%); gMean = Geometric Mean; gSD = Geometric SD; LLOQ = Lower Limit of Quantification; n = number of subjects by treatment group at each visit for the parameter; N = number of subjects per treatment group; ; NC = not calculable; NGF = Nerve-Growth Factor; NQ = not quantifiable.

Note: serum total NGF concentration units = pg/mL

Reference Listing: 16.2.10.2

^[1] Baseline is defined as the last observation recorded prior to the first dose of treatment.

[figure not shown]

Programming Notes:

- Repeat for ADA Status: "ADA Positive", "ADA Negative" and "Overall".
- Include the following timepoints: Baseline (Day 1), Week 2, Week 4, Week 6, Week 8, Week 10: Pre-Dose, Week 10; Before End of Infusion, Week 10: 8 Hours after Infusion, Week 10 + 24 hours, Week 11, Week 12; Week 18.
- A column for column dosing (column dosing (column dosing (column dosing (column dosing dosi

Final 1 2 | 04-Oct-2023 | Page 134 of 218

[figure not shown]

Planned Listing Descriptions and Shells

Number T	itle	Population	Unique (U) or Repeated (R)
Listing 16.2.1.1	1 - S ub	ject Disposition - Screening Population	U
Listing 16.2.1.2	2 - Ass	ignment to Analysis Populations - Screening Population	U
Listing 16.2.1.3	3 - Rea	son for IP Discontinuation and Withdrawal from the Study - Safety Population	U
Listing 16.2.1.4	4 - List	of Reasons for Screening Failure - Screen Failure Population	U
Listing 16.2.1.5	5 - Sub	ject Visits and COVID-19 Impact - Screening Population	U
Listing 16.2.2.1	1 - Sub	jects Not Meeting All Inclusion Criteria or Meeting any Exclusion Criteria - Screening Population	U
		ocol Deviations - Sa fety Population Error! Reference source not found. Error! Reference source not found. Error! round. Error! Reference source not found.	U
		omization and Treatment Group - Safety Population Error! Reference source not found. Error! Reference source ference source not found. Error! Reference source not found.	U
Listing 16.2.4.1	1 - Der	nographic and Baseline Characteristics - Screening Population	U
Listing 16.2.4.2	2 - Me	dical History - Safety Population	U

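### Table 14.3.5.20 can count a subject with a missing baseline ADA result in n but not in Nobs, which overstates TE-ADA incidence if any such subject later tests positive

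*SAP*

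**What the plan says.** The passages are in the Final 1.2 shell of Table 14.3.5.20, under SAP section 6.5.

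- **Numerator, footnote [1]:** "n represents the number of subjects satisfying the conditions of the specified ADA category". Nothing limits n to members of Nobs.
- **Denominator, footnote [3]:** "Nobs represents the number of subjects with an ADA result at baseline and at least one post-baseline ADA assessment".
- **Category, footnote [5]:** "TE-ADA positive is defined as either ADA negative at baseline and post-baseline ADA positive (Treatment Induced ADA Positive", with boosting of a positive baseline as the other route. The same footnote adds "ADA incidence is the proportion of TE-ADA+ subjects in a population".
- **Persistent and transient, footnotes [7] and [8]:** both start from a negative baseline: "ADA negative at baseline and having at least 2 post-baseline ADA positive measurements" and "ADA negative at baseline and at least one post-baseline ADA positive measurement and not fulfilling the conditions for persistently positive".
- **Programming note:** "It is assumed that participants with a missing baseline ADA result are ADA negative at baseline".

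The TE-ADA, treatment-induced, TE-persistent and TE-transient rows all carry footnotes [1] and [3].

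**The concern.** The note and footnote [3] treat the same subject differently. The note gives a subject without a baseline sample a negative status, which lets that subject qualify as treatment-emergent. Footnote [3] asks for an actual baseline result and keeps the subject out of the denominator. A proportion built this way is not the share of any defined group. Its error goes in one direction, upward, and in the extreme it can pass 100%. The figure affected is the one the table labels as ADA incidence, in a trial with small arms where one subject moves a percentage visibly. Two programmers could also read these lines differently and report different incidences.

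**Working it through.** The table is an empty shell, so there is no stated figure to reproduce. The check is algebra on the definitions, followed by an illustration with assumed counts.

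**Notation**
- N = subjects with a baseline result and a post-baseline result (Nobs by footnote [3])
- a = TE-ADA positives among those N
- m = subjects with no baseline result but at least one post-baseline result
- m+ = those of the m who are positive post-baseline

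**Three versions of the incidence**
1. As written: (a + m+)/N
2. Imputed subjects in both parts: (a + m+)/(N + m)
3. Imputed subjects in neither part: a/N

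**Direction.** If m+ ≥ 1, then m ≥ 1, so version 1 exceeds version 2 by the factor (N + m)/N. It exceeds version 3 by m+/N. If m = 0, all three agree.

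**Rows affected.** A missing-baseline subject with a later positive adds one to the TE-ADA row, one to the treatment-induced row, and one to either the persistent or the transient row. The prevalence row is not affected, because footnote [2] accepts a result at any time. The treatment-boosted row and the row for subjects positive both at baseline and afterwards need a positive baseline, so no imputed subject enters their n.

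**Illustration.** The SAP gives no arm sizes for this table and no ADA counts. The Table 14.2.1.1.1 footnote reports 106 mITT subjects at Week 2. Over four groups that is 106/4 = 26.5, so I assume 27 per arm with post-baseline ADA data. I also assume a = 4 and m = m+ = 1, so N = 26.

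| Version | Calculation | Result |
|---|---|---|
| As written | (4 + 1)/26 | 19.2% |
| In both parts | (4 + 1)/27 | 18.5% |
| In neither part | 4/26 | 15.4% |

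The mismatch itself is worth 19.2 − 18.5 = 0.7 points. The further step from 18.5% to 15.4%, 3.1 points, is the effect of the imputation, which is a separate choice.

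**Sensitivity to m, arm of 27.** The inflation factor over version 2 is 27/26 = 1.04 for m = 1, 27/25 = 1.08 for m = 2, and 27/23 = 1.17 for m = 4.

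**Extreme case.** If all 27 subjects are positive and one has no baseline, the table would print 27/26 = 103.8%.

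**The case against.** The strongest reply is that the overstatement depends on how the lines are read. A programmer could take the assumed negative status as a baseline result and put the subject in Nobs. Or n could be restricted to Nobs, as the n/Nobs layout suggests. Either way n would be a subset of Nobs.

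Neither reading is stated, and neither leaves the text intact. If an imputed status counts as a result, every subject has one at baseline. Footnote [4], "Nobs represents the number of subjects with an ADA result at baseline", would then exclude nobody, and nor would footnote [2]. If n is limited to Nobs, the note does nothing in the rows that use [3]. The text needs a change under any reading.

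Other parts of the reply stand:

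- The footnote to Table 14.3.1.5 says that the ADA categories are defined in the SAP, and the part of the SAP that would hold those definitions is not at hand. It may settle the matter, but nothing visible in these shells does.
- The size is unknown and may be zero. Larger gaps appear only with several missing baselines, and the largest only if all of those subjects later test positive.
- The table is descriptive, with no test or decision rule shown. It prints n beside Nobs, and Listing 16.2.9.19 gives ADA results by subject and visit, so affected subjects can be traced.

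A reader might also infer a matching fault in footnote [4], which serves the row for subjects positive only at baseline. The documents do not support that. A subject in that row must have a positive baseline result, so every member of n is in Nobs.

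**Conclusion.** The inconsistency is real. Followed literally, the programming note with footnotes [1] and [5] to [8] puts a subject in n whom footnote [3] leaves out of Nobs. If at least one subject has a missing baseline and a post-baseline positive, the four rows that allow a negative baseline are overstated. In the assumed arm of 27 with one such subject and 4 other positives, the table shows 19.2% against 18.5% or 15.4% under a consistent rule.

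A reader might infer that reported incidence is certainly biased. The SAP gives no count of missing baselines, so only the conditional statement is supported. Nor does anything shown make TE-ADA incidence the leading immunogenicity result. The assumption that a missing baseline is negative is a stated choice that can be kept; the fault is that it is applied to one part of the fraction only.

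**What to change.** Apply one rule to n and Nobs in every row that uses footnote [3]. Either option is coherent:

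1. **Keep the assumption.** Redefine Nobs [3] as subjects with at least one post-baseline ADA result, and say that a missing baseline is taken as negative.
2. **Drop the assumption.** Delete the programming note and state that n as well as Nobs requires an observed baseline and a post-baseline result. This must cover the non-TE-ADA row too. Without the note, footnote [6] would otherwise pick up a missing-baseline subject with a later positive, and the mismatch would move to that row.

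Use the same classification in Table 14.3.1.5, which tabulates adverse events by these categories. Reporting the number of missing baselines in a footnote would show whether the choice matters. Footnote [4] needs no change. The cost is a footnote, a programming note and the matching program logic, with no new data.
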